7.3 Participant Enrollment and Follow-Up

This project aims to enroll approximately 6,400 subjects per year for two study areas (total for *W. bancrofti* and *B. timori* sub-projects). Each of the two study areas (one for *Brugia and Wuchereria (Sikka)* and one for *Wuchereria (Java)*) will have cluster surveys of approximately 400 people per village for 4 villages from annual MDA areas and 400 people per village for 4 villages from twice per year MDA areas.

The community/household surveys are cross-sectional with no follow-up planned.

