7.4 Statistical Analysis Plan

The following outcome variables will be collected and treated as binary variables: Microfilaremia, antigenemia with the Binax Now Filariasis Card Test and/or the Alere Filariasis Strip Test, anti-filarial antibody (*Brugia* endemic area only) and stool parasites (separate analysis for *Ascaris*, *Trichuris*, and Hookworm). Microfilaria counts (recorded as

MF/60 µl smear) and stool egg counts per species (recorded as eggs/gram of feces) will be taken as count variables.

Data will also be collected for demographic characteristics and covariates including age, gender, history of lymphedema, scrotal swelling (hydrocele), and prior treatment for LF.

For demographic characteristics variables, descriptive statistics will be examined for the individuals who participate in the trials by sentinel site (village) and over years of observation. Frequency will be tabulated for categorical variables. Descriptive statistics (mean, median, range and standard deviation) will be obtained for continuous variables.

Impact of MDA on study outcome measures

1. Testing primary hypothesis

The primary hypothesis is that twice annual MDA is superior to annual MDA for eliminating LF. The binary outcome variables used to test this hypothesis include microfilaremia and antigenemia and anti-filarial antibody (*Brugia* endemic area only). The model which is being used will fit a linear trend over time within each village. The mean slope across villages within each treatment group will then allow estimates of time to target levels for control (microfilaremia < .5% and antigenemia < 2%) for a selection of baseline prevalences. To illustrate the analysis strategy, we use antigenemia as an example.

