The antigenemia prevalence is expressed as filarial antigenemia rate (proportion of examined individuals with filarial parasite antigenemia detected with the Binax Now Filariasis Card Test). To estimate the effect of MDA on antigenemia prevalence, we will tabulate mean rates of antigenemia across the four sentinel sites from each treatment zone (annual vs. twice annual MDA) over years of observation including the baseline. A generalized linear mixed model (GLMM) **with a logistic link function** will be used to account for the correlation of observations clustered within the same household from the same sentinel site. The model to estimate the difference in the odds of antigenemia includes treatment regimen and year of observation, and interaction between treatment regimen and year of observation. Some covariates that will be adjusted for in the analysis include sentinel sites, history of lymphedema, scrotal swelling (hydrocele) and prior treatment for LF as well as demographic variables of interest. Modeling will be performed with use of PROC GLIMMIX in SAS 9.2. CONTRAST statements will be used to test the significance of the log odds of antigenemia between the two treatment regimens at each year of observation. The difference of slope of rate decrease between the two regimens over the years of observations will also be tested with CONTRAST statements in PROC GLIMMIX. The resulting estimates will be converted to odds ratios with 95% confidence interval calculated from the robust estimator of variance. The other binary outcome variables (microfilaremia and anti-filarial antibody) will be analyzed with the same technique.

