With microfilaria (per 60 μ l of blood) measured as counts, we will display mean counts of microfilaria across the four sentinel sites from each treatment zone (annual vs. twice annual MDA) over years of observation including the baseline. To accommodate zero counts in modeling, we will use Geometric mean intensity (GMI) of circulating microfilaria. GMI is calculated as $\text{antilog}[(\sum \log(x+1))/n] - 1$, where x is the number of microfilaria per 60 mm^3 of blood and n is number of subjects. A generalized linear mixed model (GLMM) (implemented in PROC GLIMMIX) will be used to account for correlation of observations resulted from clustering. CONTRAST statements will be used to test the significance of differences in GMI of antigenemia between the two treatment regimens at each year of observation. The resulting estimates of GMI will be presented with 95% confidence interval. All statistical tests will be two-sided at a significance level of 0.05, but one-sided p-value will be reported according to the hypothesis. Similar analytic models will be done for community Mf loads and community egg load for each of three intestinal worm eggs.

The cost analysis comparing the two treatment regimens will be conducted by [name] of the George Washington University School of Public Health and Health Services. The model will also allow cost effectiveness analysis when combined with the efficacy analysis.

2. Testing secondary hypothesis

The secondary hypothesis is that twice annual MDA is superior to annual MDA in controlling STH. The primary endpoint for assessing the impact of MDA on STH infections is community egg load (average stool egg count per species). The analysis strategy for these end points is the same for microfilaria count in testing the primary hypothesis.

Adverse event

Since this is a minimal risk and nonintervention study, adverse events are not expected to be an issue. However, subjects will be monitored for adverse events related to blood collection. Proportion of subjects with an adverse event will be tabulated with 95% confidence interval for each sentinel site at each year of observation.

Treatment coverage rate

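### The primary LF hypothesis has several outcomes and contrasts, all at 0.05, with no deciding outcome, multiplicity rule or rule for combining the two areas

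*Combined protocol and SAP*

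**What the plan says.** All references are to the combined protocol and SAP.

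- **Outcomes.** Section 7.4 states one primary hypothesis, that 2X MDA is superior to 1X for eliminating LF, and continues: "The binary outcome variables used to test this hypothesis include microfilaremia and antigenemia and anti-filarial antibody", the last only in the Brugia-endemic area. Antigenemia is then worked through as an example. It is not designated as the deciding outcome.
- **Slope.** A linear trend is fitted in each village. "The mean slope across villages within each treatment group will then allow estimates of time to target levels for control", the targets being microfilaremia below 0.5% and antigenemia below 2%.
- **Contrasts.** CONTRAST statements will "test the significance of the log odds of antigenemia between the two treatment regimens at each year of observation". Then: "The difference of slope of rate decrease between the two regimens over the years of observations will also be tested". The other binary outcomes are handled in the same way.
- **Counts.** Under the same hypothesis, the paragraph on microfilaria counts adds tests of "differences in GMI of antigenemia between the two treatment regimens at each year of observation".
- **Error level.** "All statistical tests will be two-sided at a significance level of 0.05, but one-sided p-value will be reported according to the hypothesis".
- **Areas.** Section 7.3: "This project aims to enroll approximately 6,400 subjects per year for two study areas". These are Sikka and Java, each with four annual and four twice-yearly villages.
- **Comparison within the plan.** For the secondary hypothesis an endpoint is named: "The primary endpoint for assessing the impact of MDA on STH infections is community egg load", by species.

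**The concern.** A claim of superiority needs a stated result that would establish it. Here one hypothesis is served by two binary outcomes in Java and three in Sikka. Each has several contrasts, and each contrast is tested at the full 0.05. The plan does not say whether one significant result is enough, whether all must agree, or which result prevails if they conflict. It also does not say whether a positive finding in one area suffices.

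The choice would then fall to whoever reads the results. Section 2.2 says the comparison is meant to show whether the efficacy of 2X justifies its extra resources, and Section 7.4 carries the efficacy result into the cost-effectiveness analysis. The success rule should therefore be fixed before the data are seen.

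**Working it through.** **1. The plan's own figure.** The only error rate given is 0.05 two-sided per test (Sections 7.2 and 7.4 agree). It is a setting, so there is nothing to reproduce. For one test it implies 0.05 / 2 = 0.025 in favour of 2X.

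**2. Number of tests.** The Protocol Summary gives a duration of 4 years but the number of surveys is not fixed, so I take 3 or 4 after baseline. If the areas are analysed separately (also an assumption), the binary outcomes give outcomes × (years + 1 slope):
- Java: 2 × (3 + 1) = 8 to 2 × (4 + 1) = 10.
- Sikka: 3 × (3 + 1) = 12 to 3 × (4 + 1) = 15.

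Yearly microfilaria-intensity contrasts add 3 or 4 per area (11-14 and 15-19 in total). The rates below leave them out.

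**3. Error by success rule, one area.** Assumptions not in the documents: no true difference, valid standard errors, outcome correlation 0.5 or 0.8, and equal between-year correlation of 0, 0.5, 0.8 or 0.9. Correlated z statistics were simulated (300,000 to 400,000 draws per setting), counting z > 1.96 in favour of 2X. The slope statistic is Σ c_t z_t divided by its standard deviation, where c_t is centred year and baseline is included.

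With categorical year, each yearly contrast is its own z_t. With linear year, it is the fitted value from a straight line through the z_t, divided by its standard deviation.

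| Success rule | Java | Sikka |
|---|---|---|
| One named slope | 2.5% | 2.5% |
| All slopes must agree | 0.4-1.1% | about 0.1-0.7% |
| Any slope suffices | 3.9-4.6% | 4.8-6.3% |
| Any yearly or slope contrast, year linear | 8.5-12.9% | 10.6-17.3% |
| Any yearly or slope contrast, year categorical | 10-19% | 12-26% |
| Bonferroni across slopes | about 2.0-2.4% | about 1.7-2.3% |

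If the outcomes were uncorrelated, any slope would give 1 − 0.975² = 4.9% in Java and 1 − 0.975³ = 7.3% in Sikka.

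**4. Two areas, one named test in each, independent.**
- Either suffices: 1 − 0.975² = 4.9%.
- Either suffices, alpha halved: 1 − 0.9875² = 2.5%.
- Both required: 0.025² = 0.06%.

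**5. One-sided p-values.** Take an odds ratio of 0.70 with one-sided p = 0.03. Then z = 1.881, SE = |ln 0.70| / 1.881 = 0.190, two-sided p = 0.06, and the 95% CI is exp(−0.357 ± 1.96 × 0.190) = 0.48 to 1.02. The one-sided p is below 0.05 while the interval includes no difference.

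**The case against.** **The slope is already the main contrast.** Section 7.4 introduces it straight after the outcomes and ties it to time to target. Yearly contrasts come in only with the worked example and its extensions. This largely stands. A reader might infer that the plan points to no contrast at all for the elimination claim, and the text does not support that. But the slope first serves an estimate of time to target, and its test is an addition to the yearly tests. If the slope does decide, two slopes in Java and three in Sikka remain unranked. On that reading the excess is modest: about 4-6% against 2.5%.

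**The higher rates depend on how year is modelled.** This stands. Section 7.4 specifies a linear trend within villages, but its account of the regimen-by-year model does not say whether year is linear or categorical. The 19% and 26% upper ends need categorical year. With linear year they fall to about 13% and 17%.

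**The correlations have no source.** This also stands. In Sikka one test detects W. bancrofti antigen and another Brugia antibody, so the correlation could lie below 0.5. The rates are illustrations.

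**The one-sided clause changes nothing.** A reader might infer that it doubles the false-positive rate. It does so only if someone applies 0.05 to the one-sided p-value. The same sentence makes the tests two-sided, which is naturally read as the deciding rule. What remains is a presentational risk.

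**Conclusion.** The point holds at moderate weight and should be addressed before analysis. Followed as written, the plan does not fix the error of the superiority claim, because the deciding outcome, the multiplicity rule and the way the areas combine are all missing.

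A reader might infer that the error is always inflated, or that this trial's false-positive rate is some figure up to 26%. The documents support neither reading. If all slopes had to agree, the rate would be below 2.5%; if any contrast sufficed, it would be well above. Every figure assumes valid standard errors. Four villages per regimen in each area is a separate threat to that assumption, and naming a primary test does not remove it.

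**What to change.** 1. **Deciding contrast.** In Section 7.4, make the already planned regimen-by-year slope difference the deciding contrast. Apply it to one outcome per area, fixed by the sponsor before analysis, or use Holm or a fixed order across the outcome slopes. Label yearly contrasts, microfilaria intensity and the remaining outcomes supportive.
2. **Areas.** State whether Java and Sikka answer separate questions, each at two-sided 0.05, or support one joint claim. If success in either area suffices, split alpha.
3. **Minor.** State that the two-sided test decides. Replace the one-sided p-value clause with two-sided p-values that match the 95% intervals.

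Two facts bear on the choice of outcome. Section 7.4 sets targets only for microfilaremia and antigenemia. If microfilaremia is chosen, Section 4 (for W. bancrofti, smears for antigen-positive persons) and Section 6.2 (smears for everyone) must first be reconciled.

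**Cost.** Items 1 to 3 are SAP wording; reconciling the smear sections may affect field work. Fewer results can be called confirmatory. Splitting alpha costs power: a test with 80% power at 0.05 has Φ(2.802 − 2.241) = 71% at 0.025. That is an illustration, since the documents give no power for 2X against 1X.

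### No change-from-baseline test is stated for egg load or MF counts, and egg load is defined as an average while the count strategy tests GMI

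*Combined protocol and SAP*

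**What the plan says.** **Endpoint.** Section 7.4, under the secondary hypothesis: "The primary endpoint for assessing the impact of MDA on STH infections is community egg load (average stool egg count per species". Section 4 (stool examination) gives the reason: the measure brings prevalence and density together.

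**Analysis of egg load.** The same part of Section 7.4 adds: "The analysis strategy for these end points is the same for microfilaria count in testing the primary hypothesis". The MF-count paragraph also says: "Similar analytic models will be done for community Mf loads and community egg load for each of three intestinal worm eggs". Neither sentence gives a scale, distribution or link.

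**The MF-count strategy.** Arithmetic means are for display: "we will display mean counts of microfilaria across the four sentinel sites from each treatment zone". For modelling, "To accommodate zero counts in modeling, we will use Geometric mean intensity (GMI) of circulating microfilaria". The contrasts test "differences in GMI of antigenemia between the two treatment regimens at each year of observation". Antigenemia is a yes/no result here, so that wording must be a slip for microfilaria.

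**Trend and slope.** The primary-hypothesis text says "The binary outcome variables used to test this hypothesis include microfilaremia and antigenemia" (plus antibody in the *Brugia* area), and then "The model which is being used will fit a linear trend over time within each village". It goes on to prevalence targets and introduces antigenemia as an illustration of the strategy. The antigenemia paragraph has a logistic mixed model with regimen, year and their interaction, adjustment for sentinel site, yearly contrasts and a slope contrast. Its last sentence extends the technique to the other binary outcomes.

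**Design.** Sections 4 and 7.3 give four villages per regimen zone in each of two areas, about 400 people per village, with surveys before and after MDA begins. Government health officials deliver the MDA. No random allocation of zones or villages is described.

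**The concern.** Two things are left open for the count outcomes.

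The first is baseline. A contrast between regimens in a single year compares the levels of two groups of four villages. If one zone has persistently lighter infection, that difference is part of the contrast whatever the drugs do. It can favour a regimen that has no advantage, or hide a real one.

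The second is the measure. An average count and a GMI weight heavy infections very differently. If the endpoint is the average and the test is on GMI, the test may answer a different question from the one the endpoint poses.

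At stake are the test of the STH hypothesis, one of two in Section 3, and the MF-count analysis under the primary hypothesis.

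**Working it through.** The documents give no sample size, power figure or data for egg counts, so there is no stated figure to reproduce.

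**1. What each contrast estimates.** Write the log load of village *j* in zone *z* (0 or 1) at survey *t* as

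y = μ_t + δz + τ_t·z + v_j + w_jt + e_jt,

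where δ is a lasting zone difference, τ_t the regimen effect (τ_0 = 0 at baseline), v_j lasting village variation, w_jt village-by-year variation and e_jt sampling error.

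- Yearly contrast: expectation δ + τ_t.
- Change from baseline: (δ + τ_t) − (δ + τ_0) = τ_t.

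The zone difference drops out only of the second.

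**2. Whether site adjustment helps.** The plan does not say whether sites are fixed or random.

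- Random or omitted: δ stays in the yearly contrast.
- Fixed: take 8 sites and 5 surveys (baseline plus four). Columns are 8 (site) + 4 (year) + 1 (regimen) + 4 (regimen-by-year) = 17, but the rank is 16, because the regimen column is the sum of its four site columns. The yearly regimen contrast is not estimable; change from baseline is.

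**3. Size of the effect, by simulation.** All inputs are assumed: one area, 4 v 4 villages of 400; zero-inflated gamma-Poisson counts (k = 0.5); 40% infected at 250 eggs/g at baseline and 20% at 150 at year 3; village SD 0.3 or 0.5 and village-by-year SD 0.2 in log load. Village-level t-tests (6 df) stand in for the mixed model. There were 4,000 runs per scenario. False rejection with no treatment effect, village SD 0.3 / 0.5:

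| Test | No gap | One zone 33% lower | One zone 50% lower |
|---|---|---|---|
| Year-3 contrast, GMI | 4.5 / 5.0% | 21.5 / 12.8% | 50.4 / 27.4% |
| Year-3 contrast, log average | 4.7 / 4.9% | 21.7 / 13.9% | 51.2 / 29.2% |
| Change in log average | 4.6 / 4.9% | 4.6 / 5.1% | 4.4 / 4.8% |
| Change in log(x+1) | 4.9 / 4.4% | 11.8 / 9.7% | 27.4 / 20.1% |
| GMI adjusted for village baseline GMI | 4.9 / 4.9% | 7.6 / 5.4% | 10.4 / 5.3% |
| Baseline contrast, GMI | 5.3 / 4.8% | 23.1 / 14.0% | 55.1 / 29.8% |

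A rerun of the year-3 GMI contrast gave 12-22% (33% gap) and 27-50% (50% gap), with about 5% for change in log average. The last row shows that a baseline contrast would often fail to flag the gap, and flagging it would not remove it.

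**4. Village-by-year variation.** With no gap and no effect, a z-test on change that used sampling variance alone rejected in 22.6 / 22.7%. A change test must therefore carry village-by-year variation.

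**5. Precision.** Leaving out sampling error, the variance of the difference with four villages per zone is (2/4)(σ_v² + σ_w²) for a yearly contrast and (2/4)(2σ_w²) for change.

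- σ_v = σ_w = 0.3: both are 0.5 × 0.18 = 0.09, SD 0.30. With sampling error the simulation gave 0.34 v 0.34, so change gains nothing.
- σ_v = 0.5, σ_w = 0.1: 0.5 × 0.26 = 0.13 (SD 0.36) v 0.5 × 0.02 = 0.01 (SD 0.10). The simulation gave 0.39 v 0.19.

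**6. Average against GMI.** For a share p infected, all at count c, the average is pc and the plan's formula gives GMI = (c+1)^p − 1.

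- p = 0.5, c = 200: average 100; GMI = 201^0.5 − 1 = 13.2.
- p = 0.1, c = 1,000: average 100; GMI = 1001^0.1 − 1 = 1.0.

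The order can even reverse: 20% at 200 (average 40, GMI 1.89) against 10% at 800 (average 80, GMI 0.95).

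**The case against.** The strongest reply is that the plan already intends a slope test for counts. Antigenemia is introduced expressly as an illustration, the trend sentence speaks of the model in general, the count paragraph uses the same software and contrast method under the same heading, and the STH section refers back to that strategy. This stands as a possible reading. Against it, the trend sentence follows a list of binary outcomes and leads to prevalence targets, and the technique is extended by name only to binary outcomes. No sentence states a slope, interaction or change test for counts.

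On the measure, the promise of similar models for community loads can be read as modelling the average itself, with GMI kept for MF intensity. That stands too, but without a scale or link the text does not settle it. GMI over all subjects also reflects both prevalence and density, so it is not an improper measure, and separate prevalence analyses by species would reveal a contrast as extreme as the one in step 6.

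The simulation has real limits. The gaps are assumed, household clustering is left out, village t-tests replace the mixed model, and only one of two areas is represented. The direction follows from step 1 without simulation; the percentages do not.

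**Conclusion.** The point holds as a gap in specification that matters and is cheap to close. For count outcomes the stated test is a yearly contrast, which carries any lasting zone difference or, with fixed sites, cannot be estimated. Under the assumed inputs, a 33% (50%) lasting gap raises false rejection at year 3 to about 12-22% (27-50%), against about 5% for change in log average. The measure to be tested for egg load is also open, and the two candidates can disagree.

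Three stronger readings are tempting and are not supported:

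- That the yearly contrast is the sole planned count test. The trend, illustration and similar-models sentences leave room for more.
- That egg load will certainly be tested on GMI. The text permits either measure.
- That the zones do differ at baseline. No document figure shows it; the absence of described randomisation only means that it cannot be ruled out.

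Nor does the check show that averages are better than GMI. The average is preferred here only because it is the endpoint as defined.

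**What to change.** In Section 7.4, for egg counts per species and for MF counts:

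- Make the main regimen test the between-regimen difference in change from the baseline survey to one named survey year (the regimen-by-year term), with a 95% confidence interval, the village as the unit of inference and village-by-year variation included. Make the yearly contrasts supportive.
- State one measure, with its scale and link, and use it for both definition and test. A ratio of average counts matches the stated endpoint. If GMI is intended, redefine community egg load that way in Sections 4 and 7.4 and adjust for each village's baseline GMI. Simple change on log(x+1) does not remove a proportional gap, and baseline adjustment removes most but not always all of it (step 3).
- Correct the clerical reference to GMI of antigenemia so that it reads microfilaria.

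The cost is wording and code, since the baseline survey is already planned. There are two downsides. Averages depend on a few heavy infections, so intervals may be wider than for GMI. Simple change gains no precision when village-by-year variation is as large as lasting village variation (step 5).

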2 BACKGROUND INFORMATION AND SCIENTIFIC RATIONALE

2.1 Background Information

Lymphatic filariasis (LF) is a deforming and disabling infectious disease that causes elephantiasis and genital deformity (especially hydroceles). The infection affects some 120 million people in 81 countries in tropical and subtropical regions with well over 1 billion people at risk of acquiring the disease [1]. LF is caused by *Wuchereria bancrofti* and *Brugia* spp. (*B. malayi* and *B. timori*), nematode parasites that are transmitted by mosquitoes. The World Health Organization (WHO) developed a plan for LF elimination that is based on using novel approaches to rapidly map endemic areas and 4 to 6 annual rounds of mass drug administration (MDA) with antifilarial medications [2, 3]. A recent report from WHO reported that more than 1.9 billion doses of MDA were distributed between 2000 and 2007 [4]. Thus, the Global Programme to Eliminate Lymphatic Filariasis (GPELF) is the largest infectious disease intervention program attempted to date based on MDA. MDA has worked better in some areas than others. A recent publication reviewed challenges faced by GPELF [5]. The limited macrofilaricidal activity of current MDA regimens (especially Ivermectin/Albendazole) that necessitate repeated annual rounds of MDA, and the difficulty of achieving high compliance rates for MDA over a period of years. ***It is clear that new dosing schedules for MDA have the potential to greatly improve the number of countries that will successfully eliminate LF by the WHO target date of 2020.***

Drugs used for LF MDA are also active against soil transmitted helminths (STH, e.g., *Ascaris*, Hookworm, and *Trichuris*). The estimated numbers of infected individuals (in millions) for *Ascaris*, hookworm and *Trichuris* range from 807-1227, 576-740, and 604-795 respectively [6]. De-worming campaigns using anthelmintics usually target special groups of the population, such as schoolchildren, and have limited impact on the transmission. Treatment of the total population and semiannual treatments may reduce re-infection considerably and will most likely lead to reduced infection densities and infection prevalences. ***Suppression of STH is an important ancillary benefit of MDA programs for filarial infections [2].***

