remain positive years after treatment has cleared microfilaremia. The antigen tests will be performed in individual residents over 5 years of age. This will be done by sampling approximately 100 randomly selected households per sentinel site (village) to produce N of 400. There will be 4 sentinel sites for each treatment zone (annual vs twice annual MDA). The target number of samples per village is close to the minimum sample size of 335 needed to show that the rate of antigenemia (card test) positivity is less than 2% (with 95% confidence and 80% power). In post-MDA populations, this corresponds to a MF rate of less than 0.5%, which is an LF elimination target. We expect to collect 4 to 5 blood samples per household. Subjects with positive card tests will be tested for microfilaremia with 60 µl night blood thick smears. Our decision to detect MF by thick smears of finger prick blood rather than membrane filtration of venous blood is because thick smears are recommended for LF elimination program guidelines. In addition, our prior studies in Egypt have shown that L3 production by *Culex* mosquitoes that feed on MF carriers with negative thick smears is negligible. The justification for collecting blood at night for MF testing is that microfilariae of *W. bancrofti* and *B. timori* in Indonesia are nocturnally periodic with highest counts in peripheral blood between 9 p.m. and 2 a.m.

Blood tests for *Brugia timori* infection *B. timori* infections will be detected by two methods, namely microscopic examination and the BrugiaRapid Test (BmR1 antibody) Cassette (Cellabs, Malaysia). Microscopic examination of thick blood smears prepared with 60 µl of blood collected between the hours of 9 p.m. and 2 a.m. The Brugia Rapid test is a rapid diagnostic test kit for detecting antibodies to filarial parasites using serum or whole blood.

Blood samples will be collected from randomly selected households per sentinel site (village) to produce N of 400. There will be 4 sentinel sites for each treatment zone (annual vs twice annual MDA). This sample size number exceeds the minimum target sample size of 335 needed to show that the MF rate is less than 2% (with 95% confidence and 80% power, assuming an actual rate of 0.5%, which is an LF elimination target). We expect to collect 4 to 5 samples per household.

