Stool examination for infection with soil transmitted helminths. We will examine stool samples of the study population mentioned above for the presence and the density of STH eggs. We will use the FLOTAC method to examine a single stool sample from each subject [10]. This quantitative method has an excellent sensitivity and will provide relatively accurate data on both prevalence and density of infection. We will use community egg loads as the primary endpoint for assessing the impact of MDA on STH infections, because this combines both prevalence and density of infection.

Hypotheses, outcomes, and methods for statistical testing are provided in Section 7, Analysis plan.

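### Does the plan test a geometric mean (GMI) when its soil-transmitted helminth endpoint is an average egg count?

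*Combined protocol and SAP*

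**What the plan says.** All references are to the combined protocol and SAP.

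- **Endpoint (Section 7.4, secondary hypothesis).** The primary STH endpoint "is community egg load (average stool egg count per species"). The stool examination paragraph of Section 4 gives the reason for choosing it: "because this combines both prevalence and density of infection".
- **Analysis (Section 7.4, secondary hypothesis).** "The analysis strategy for these end points is the same for microfilaria count in testing the primary hypothesis".
- **The microfilaria-count strategy (Section 7.4, primary hypothesis).** Arithmetic means are descriptive: "we will display mean counts of microfilaria across the four sentinel sites". Because of the zeros, modelling uses the GMI, which is the antilog of the mean of log(x+1), minus 1, with n the number of subjects. On testing, it says: "CONTRAST statements will be used to test the significance of differences in GMI of antigenemia between the two treatment regimens". The GMI estimates carry the 95% confidence interval.
- **Extension to loads (same paragraph).** "Similar analytic models will be done for community Mf loads and community egg load for each of three intestinal worm eggs".

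No distribution or link is given for any count model, and the word average is not qualified as arithmetic or geometric.

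**The concern.** Most readers take an average egg count to be an arithmetic mean. The same section displays mean counts and tests the GMI, so it seems to treat them as two quantities. If the STH analysis copies the microfilaria analysis, the p-value and interval belong to the GMI while the endpoint is named as an average. If only the mixed-model framework carries over, the tested mean, the distribution and the link for egg load are all unstated.

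What would be at stake is the STH conclusion. It could be worded as a reduction in average egg count and supported by a test of something else, or the choice of mean could be made after the data are seen. The displayed means and the planned binary analyses by species would show a reader that something differed, but neither gives a test or interval for the mean load.

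**Working it through.** The plan states no figure on this point, so there is none to reproduce. The check asks how far the two means can differ, when they do, and what the alternative test costs. **All egg-count distributions are assumed, because the documents give none.**

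**1. Two-point illustration.** Let a proportion p be positive, all at x eggs per gram (epg). Then load = p·x and GMI = (x+1)^p − 1. The starting point is p = 0.50, x = 200: load 100, GMI = 201^0.5 − 1 = 13.18.

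| Change | Load | GMI | Change in GMI |
|---|---|---|---|
| Prevalence halved (0.25, 200) | 50 | 201^0.25 − 1 = 2.77 | −79% |
| Intensity halved (0.50, 100) | 50 | 101^0.5 − 1 = 9.05 | −31% |
| Both × 0.707 (0.3536, 141.4) | 50 | 142.4^0.3536 − 1 = 4.77 | −64% |
| Offsetting (0.40, 250) | 100 | 251^0.40 − 1 = 8.12 | −38% |
| Offsetting (0.45, 222) | 99.9 | 223^0.45 − 1 = 10.40 | −21% |

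In the first three rows both measures fall, by different amounts. They disagree on whether anything changed only in the last two rows, where prevalence falls and intensity among positives rises by the offsetting amount.

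**2. Reversal is possible but needs the same pattern.** Take two samples of 1,600 (4 villages × 400). In the first, 1,200 are zero, 360 are at 100 and 40 at 1,000 epg: mean 47.5, GMI 2.36. In the second, 1,400 are zero, 129 are at 100 and 71 at 1,000 epg: mean 52.4, GMI 0.97. The mean is 10% higher and the GMI 59% lower. Prevalence is halved (25% to 12.5%) while heavy infections rise from 40 to 71.

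**3. What the plan expects.** Section 2.1 says that treating the whole population and treating twice a year "will most likely lead to reduced infection densities and infection prevalences". That is the pattern in which the two measures usually agree in direction.

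**4. Rejection rates with equal arithmetic load.** One simulation took its sample structure from Section 4 ("approximately 100 randomly selected households per sentinel site (village) to produce N of 400"), with 4 villages × 100 households × 4 people per regimen. It used household-level standard errors and no village effect. For 50% at 200 versus 40% at 250 epg, the log(x+1) test rejected in 88-99% of runs and the ratio of means in 5-9%. For 50% at 200 versus 45% at 222 epg, the figures were about 35-59% and 4-9%.

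These figures leave out variation between villages. A second simulation (1,500 runs, 4 villages × 400 per regimen, log-SD 1 or 2 among positives) used a t-test on village means of log(x+1), with village SD 0.2-0.5 on logit prevalence and log intensity. The first case then rejected in about 10-36% of runs, against 82-96% with no village effect. The second case rejected in about 6-13%. The GMIs still differ in truth; a village-level comparison with four villages per regimen simply has little power to declare it.

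**5. Cost of testing the arithmetic mean instead.** With the setup of the first simulation in step 4 and a true 50% fall in load, at log-SD 2 among positives:

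- ratio of means: power 66-79%
- log(x+1): power 98-100%

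At log-SD 1 both reach 98% or more. The error rate of the ratio-of-means test rose to about 9% at log-SD 2. A negative-binomial mixed model, the obvious way to test means, was not simulated, and robust standard errors would rest on 8 villages per study area.

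**The case for a change.** The strongest case for a change is that the sentence on similar models does not settle the matter. The only count model described is the GMI one, so similar means either GMI again or something unspecified. Both hypotheses in Section 3 are superiority claims, and a few sentences naming the mean, link and contrast would remove the choice at no cost in data.

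Part of this stands. The plan does not say which mean community egg load is, and gives no distribution or link. The wording about the GMI of antigenemia adds to the untidiness, but it is evidently a slip for microfilaria, since antigenemia is a binary outcome.

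What does not stand is the stronger reading, that the plan tests the wrong quantity or provides no test of its endpoint. Community egg load is named as something to be modelled. A geometric mean over all subjects is also an average. It falls when either prevalence or density falls, which meets the reason in Section 4, and that reason sets no relative weights for the two. Using log(x+1) for skewed counts with many zeros is a stated and defensible choice.

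**Conclusion.** No change to the plan is needed. The gap is a missing label on the word average, and following the text as written fills it sensibly: a log(x+1) mixed-model comparison by species, reported as GMI with its interval, beside the displayed arithmetic means and the planned binary analyses. That is a valid comparison of regimens on a quantity combining prevalence and density, provided its result is described as a GMI effect.

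The size is limited. Only the secondary (STH) hypothesis and the load summaries are involved; the binary filariasis outcomes are untouched. The two means differ in size under any of the assumed distributions. They conflict in conclusion only where prevalence and intensity move in opposite directions, contrary to what Section 2.1 expects. Moving the test to arithmetic means would be a trade-off that statisticians could argue either way, with a real loss of power under heavy skew (66-79% against 98-100%), and not a correction.

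This rests on assumed egg-count distributions and assumed village variation, and on reading average as compatible with a geometric mean, which the documents neither state nor exclude.
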